4 STUDY DESIGN

4.1 Overall Design

This is a partially blinded, randomized, active-controlled, multi-site study to evaluate the safety, tolerability, and efficacy of MK-1654 versus palivizumab and the PK of MK-1654 in infants who are eligible and recommended to receive palivizumab in their first RSV season. Part 1 of the study will be double-blind, and Part 2 will be open-label (see Section 1.3). A secondary purpose of the study is to evaluate the safety, efficacy, and PK of a dose of MK-1654 administered at the start of the second RSV season (RSV Season 2) for eligible participants in either treatment group who continue to be at increased risk of RSV who are entering their second RSV season (see Section 5.1 and Section 5.2).

The Sponsor estimates that the study will require approximately 5 years from the time that documented informed consent is provided for the first participant until the last participant's last study-related contact or visit.

Overall, 1000 participants will be randomized in a 1:1 ratio to receive MK-1654 or palivizumab on RSV Season 1 Day 1 (double-blind). Randomization will be stratified according to the following factors:

1. Region:

- Northern Hemisphere
- Southern Hemisphere

2. Participant condition (see Section 5.1, Inclusion Criteria #1):

- CLD (≥ 200 infants)
- CHD (≥ 100 infants)
- Neither CLD nor CHD < 29 weeks gestational age
- Neither CLD nor CHD ≥ 29 weeks gestational age

Infants 0 through 8 months (ie, up to 8 months and 29 days) of age at the time of consent will comprise at least 90% of the participants. Enrollment will begin during the 4 weeks before the estimated onset of the RSV season and will end before the estimated peak of the RSV season (approximately a 17-week duration during a routine RSV season; see Section 4.2.1.1.1). Infants born before the RSV season should be enrolled before the onset of the RSV season. Infants born during the RSV season should be enrolled as soon as possible after birth. Special considerations for RSV season determination in tropical and subtropical regions, as well as disrupted RSV seasonality (eg, due to COVID-19), are in the regional RSV seasonality guidance document (or equivalent).

CLD and CHD participants will be eligible and consented for inclusion in 2 RSV seasons. Participants in the Early or Moderate Pre-term Group who meet the additional inclusion criteria for RSV Season 2 (see Section 5.1) will also be consented for participation in 2 RSV seasons.

All study participants will receive 2 blinded doses before unblinding in RSV Season 1:

- MK-1654 group: MK-1654 (Dose 1) and placebo (Dose 2)
- Palivizumab group: palivizumab (Dose 1 and Dose 2)

All participants, irrespective of treatment group, will have safety monitoring (AEs and SAEs), efficacy surveillance to monitor the incidence of RSV-associated MALRI and hospitalization, and blood sample collection as described in the SoA (see Section 1.3.1.1 SoA – RSV Season 1 Part 1).

Participant's treatment assignment will be unblinded at the Day 60 visit before any visit procedures. Participants in the MK-1654 group do not have any additional planned doses in RSV Season 1 and will continue with safety monitoring, efficacy surveillance, and blood sample collection as described in the SoA (see Section 1.3.1.2 SoA – RSV Season 1 Part 2 – MK-1654 Group). Participants in the palivizumab group will receive at least 3 and up to 5 single doses of palivizumab, once every 28 (+4) days (inclusive of dosing day; minimum of 28 days between doses), depending on the timing of enrollment relative to the RSV season. For calculating the visit windows for subsequent administrations, the day of the previous administration is considered Day 1. These participants will continue with safety monitoring and efficacy surveillance as described in the SoA (see Section 1.3.1.3 SoA – RSV Season 1 Part 2 – Palivizumab Group).

For infants enrolled and consented to participate in RSV Seasons 1 and 2, inclusion/exclusion criteria will be rechecked at the Day 240 visit for eligibility to continue in RSV Season 2 (see Section 5.1 and Section 5.2). Participants still eligible will begin the RSV Season 2 between 246 to 393 days after RSV Season 1 Dose 1, depending on the timing of enrollment relative to the RSV season (see Section 8.1.8.1). Participants in the palivizumab group who are continuing in RSV Season 2 will have blood sample collection at the Day 240 visit to serve as the baseline for RSV Season 2. All participants not continuing in RSV Season 2 will be monitored for safety for 365 days after receiving the first dose in RSV Season 1.

For participants continuing in RSV Season 2, a dose of MK-1654 will be administered (open-label) up to 4 weeks before the beginning of the participant's second RSV season (246 to 393 days after Dose 1 in RSV Season 1 during a routine RSV season). For participants who received MK-1654 in RSV Season 1, this will be a second dose. For participants who received palivizumab in RSV Season 1, this will be the first dose of MK-1654. Participants in RSV Season 2 will be followed for 180 days after the RSV Season 2 dose, including safety monitoring (AEs and SAEs), efficacy surveillance to monitor the incidence of RSV-associated MALRI and hospitalization, and blood sample collection as described in the SoA (see Section 1.3.2 SoA – RSV Season 2).

If during the RSV season a participant undergoes 1) ECMO or 2) surgical intervention for CHD and requires cardiopulmonary bypass during the procedure, Sponsor consultation will need to occur. The Sponsor consultation may determine that the participant receive an additional post-surgery dose of MK-1654 or palivizumab at the recommended dose based on their randomization allocation and the RSV season at the time of the procedure (see Section 8.1.8.1). The post-surgery follow-up activities are described in the SoAs (see Section 1.3) and in the guidance document provided by the Sponsor.

An IA is planned for this study and will be conducted by an external unblinded statistician and reviewed by an eDMC (see Section 10.1.4.3). The IA will occur after the first 30 participants are randomized (and after the Day 42 contact for safety follow-up) or after the first hemisphere enrollment (~17 weeks) is complete in the initial RSV season of the study, whichever occurs first to conduct an early assessment of safety. In addition to this IA, the eDMC will review available safety and RSV disease incidence data from this study approximately every 6 months (see Section 9.7).

Specific procedures to be performed during the study, as well as their prescribed times and associated visit windows, are outlined in the SoA in Section 1.3. Details of each procedure are provided in Section 8.

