1.3.1 RSV Season 1 Schedule of Activities

1.3.1.1 Schedule of Activities RSV Season 1 Day 1 Up to Day 60 Visit (All Participants; Part 1 – Double-blind)

Study Period	Screening, Randomization, and Intervention			Follow-up RSV Season 1 (Day 1 Up to Day 60 Visit)							Notes
Visit Number/Title	1			TC	2	Weekly contact start	3	TC	4A	UNSCH	See Section 8.13 for descriptions of study visits. UNSCH for respiratory infection and AESI assessment and early withdrawal, if indicated.
RSV Season 1 All Participants Part 1 Scheduled Day and Window (Days):	Day 1			3 (-1) ^a	7 (+2)	14 (±2 ^b)	28 (+4)	42 (+4) ^c	60 ^d (see Section 1.3.1.2 and Section 1.3.1.3)	If indicated	^a If Day 3 is not a business day, the phone call should occur on Day 2. ^b ±2-day window applies to all weekly contacts. ^c At least 14 days after Dose 2. ^d Participant’s treatment assignment will be unblinded at the Day 60 visit (28-32 days after Dose 2).
	Predose	Dose	Post-dose								
Administrative Procedures											
Informed Consent	X										Participants consented for 1 or 2 RSV seasons depending on eligibility (see Section 5.1 and Section 5.2).
Informed Consent for FBR	X										Participation in FBR is optional and consent must be obtained before collection of buccal swab DNA samples.
Inclusion/Exclusion Criteria	X										
Participant Identification Card	X										Randomization number will be added to the card.
Medical History	X										
Prior/Concomitant Medication Review	X		X	X	X	X	X	X		X	Concomitant medications will be collected from Day 1 to 14 days after Dose 2, afterwards only concomitant medications associated with an AE/SAE will be recorded.
Predose NP Sample Collection for RT-PCR Testing	X (if indicated)										Collect if respiratory infection symptoms are present within 7 days before the Day 1 visit. See Section 8.13.1.1 and Section 8.2.3.
Assignment of Randomization Number	X										

Study Period	Screening, Randomization, and Intervention			Follow-up RSV Season 1 (Day 1 Up to Day 60 Visit)						Notes	
Visit Number/Title	1			TC	2	Weekly contact start	3	TC	4A	UNSCH	See Section 8.13 for descriptions of study visits. UNSCH for respiratory infection and AESI assessment and early withdrawal, if indicated.

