AESI Assessment		X (if indicated)							X	Required if indicated AESI require further assessment. See Section 8.4.8.	
Venous Blood for ADA and Additional ADA Characterization				X (if indicated)					X	Collect only if participant experiences a Grade 3 or 4 anaphylaxis/hypersensitivity AESI through Day 42. See Section 8.4.8.1 and Section 10.2 (Appendix 2).	
Respiratory Virus Assessments											
Surveillance for Respiratory Infection Symptoms				X	X	←Weekly Contact→					Determine if participant had respiratory symptoms or was seen in a clinical setting. See Section 8.2.1.
Respiratory Infection Assessment			X (if indicated)							X	Required if respiratory infection symptoms require further assessment. See Section 8.2.2.
NP Sample Collection for RT-PCR Testing				X (if indicated)					X	Collect if respiratory infection symptoms are observed. See Section 8.2.2.2 and Section 8.2.3.	
Pharmacokinetics/Immunogenicity/Pharmacodynamics											
Venous Blood for MK-1654 PK	X				X						
Venous Blood for ADA	X										
Venous Blood for RSV SNA	X				X						
Future Biomedical Research											
Buccal Swabs (DNA) for FBR	X										Should be obtained predose on randomized and FBR-consented participants only. However, it can be collected at any later study visit after randomization.

ADA=antidrug antibodies; AE=adverse event; AESI=adverse event of special interest; DNA=deoxyribonucleic acid; eDiary=electronic diary; FBR=future biomedical research; LAR=legally acceptable representative; NP=nasopharyngeal; PK=pharmacokinetics; RSV=respiratory syncytial virus; RT-PCR=reverse transcriptase-polymerase chain reaction; SAE=serious adverse event; SNA=serum neutralizing antibodies against RSV; TC=telephone call; UNSCH=unscheduled visit.

1.3.1.2 Schedule of Activities RSV Season 1 Day 60 Visit Through End of RSV Season 1 (MK-1654 Group; Part 2 – Open-label)

Study Period	Follow-up RSV Season 1 (Day 60 Visit through end of RSV Season 1)							Notes
Visit Number/Title	4A	5	Weekly contact ends	6	TC	Post-surgery Follow-up	UNSCH	See Section 8.13 for description of study visits. Post-surgery follow-up visit for participants who undergo 1) ECMO or 2) surgical intervention and require cardiopulmonary bypass during the procedure for CHD during the RSV season and are recommended during Sponsor consultation to receive additional study intervention (Section 8.1.8.1). UNSCH for respiratory infection and AESI assessment and early withdrawal, if indicated.

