RSV Season 1 MK-1654 Group Part 2 Scheduled Day and Window (Days):	60 (28-32 days after Dose 2)	150 (±5)	180 (±2 ^a)	240 (±5)	365 (+14) ^b	If indicated	If indicated	See SoA in Section 1.3.1.1 for activities before the Day 60 visit. Participant's treatment assignment will be unblinded at the Day 60 visit (28-32 days after Dose 2). ^a Continue weekly contact, each with a ±2-day window. ^b Participants continuing into RSV Season 2 will begin RSV Season 2 up to 4 weeks before the start of their second RSV season (246 to 393 days after RSV Season 1 Dose 1) (Section 4.2.1.1.1). See SoA in Section 1.3.2 for RSV Season 2. Participants not eligible for RSV Season 2 will be followed through the RSV Season 1 Day 365 TC.
Administrative Procedures								
Concomitant Medication Review	X	X	X	X	X	X ^c	X	Only concomitant medications associated with an AE/SAE will be recorded. ^c Concomitant medications will be collected for 42 days following an additional post-surgery dose of MK-1654.
MK-1654 Administration						X		See Section 6.1, Section 6.2, and Section 8.1.8.1.
Provide or Reactivate Device for eDiary Data Collection and Provide LAR Training						X		For participants using a study-provided device, provide eDiary if LAR previously returned the original study-provided device.
Review eDiary with LAR						X		Safety follow-up for 42 days after post-surgery dose. See Section 8.3.5.
Collect eDiary Device from LAR				X				
Review Inclusion/Exclusion Criteria				X				For participants enrolled in 2 RSV seasons, review inclusion/exclusion criteria for RSV Season 2 to ensure participant meets RSV Season 2 eligibility requirements. See Section 5.1.1 and Section 5.2.1.

Study Period	Follow-up RSV Season 1 (Day 60 Visit through end of RSV Season 1)							Notes
Visit Number/Title	4A	5	Weekly contact ends	6	TC	Post-surgery Follow-up	UNSCH	See Section 8.13 for description of study visits. Post-surgery follow-up visit for participants who undergo 1) ECMO or 2) surgical intervention and require cardiopulmonary bypass during the procedure for CHD during the RSV season and are recommended during Sponsor consultation to receive additional study intervention (Section 8.1.8.1). UNSCH for respiratory infection and AESI assessment and early withdrawal, if indicated.

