3 HYPOTHESES, OBJECTIVES, AND ENDPOINTS

This is an estimation study without hypotheses. The following objectives will be evaluated in the study population. The RSV Season 1 42-day safety follow-up period consists of safety data collected from Day 1 post Dose 1 through 14 days post Dose 2.

Primary Objectives	Primary Endpoints

 RSV Season 1: To evaluate the safety and tolerability of MK-1654 compared to palivizumab in RSV Season 1 as assessed by the proportion of participants experiencing AEs. 	
 Solicited injection-site AEs from Days 1 through 5 after each dose Solicited daily body temperature, with fever defined as rectal temperature $\geq 102.2^{\circ}\text{F}$ ($\geq 39.0^{\circ}\text{C}$) or axillary temperature $\geq 101.7^{\circ}\text{F}$ ($\geq 38.7^{\circ}\text{C}$) from Days 1 through 5 after each dose Solicited systemic AEs from Days 1 through 5 after each dose Anaphylaxis/hypersensitivity AESI from Days 1 through 42 post Dose 1 Rash AESI from Days 1 through 42 post Dose 1 Nonserious AEs from Days 1 through 42 post Dose 1 and 14 days after each subsequent dose SAEs through the duration of participation in RSV Season 1
Secondary Objectives	Secondary Endpoints

 RSV Season 1: To estimate the efficacy of MK-1654 compared to palivizumab as assessed by the incidence of RSV-associated MALRI (outpatient and inpatient) from Days 1 through 150 post Dose 1 in RSV Season 1. 	
 RSV-associated MALRI (outpatient and inpatient), defined as the following seen in an outpatient or inpatient clinical setting: 
 Cough or difficulty breathing; AND 
 1 or more of the following: wheezing, chest wall in-drawing/retractions, rales/crackles, hypoxemia, tachypnea, dehydration due to respiratory symptoms; AND 
 RSV-positive RT-PCR NP sample

 • RSV Season 1: To estimate the incidence of RSV-associated hospitalizations from Days 1 through 150 post Dose 1 in RSV Season 1 in the MK-1654 and palivizumab groups. 	
 • RSV-associated hospitalization, defined as the following: 
 ▪ Hospital admission for respiratory illness; AND 
 ▪ RSV-positive RT-PCR NP sample

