6.3.3 Blinding

In Part 1 of this study (up to the Day 60 visit), a double-blinding technique will be used. MK-1654, palivizumab, and placebo will be prepared and administered in a blinded fashion by an unblinded pharmacist or medically qualified study personnel not otherwise involved in the conduct of the study. Unblinded study personnel should not have contact with participants for any study-related procedures/assessments postdose (prior to unblinding), including all safety follow-up procedures. The participant's legally acceptable representative,

the investigator(s), and Sponsor personnel or delegate(s) will be unaware of the study intervention assignments.

Part 2 of this study (time of unblinding through duration of participation in the study) is conducted as open-label therefore, the Sponsor, investigator, and participant/participant's legally acceptable representative will know the intervention administered.

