9.2 Responsibility for Analyses/In-house Blinding

The statistical analysis of the data obtained from this study will be the responsibility of the Clinical Biostatistics department of the Sponsor.

This study will be conducted as a double-blind study under in-house blinding procedures until the Sponsor study team, investigators, and participants are unblinded to the participant's treatment assignment at the RSV Season 1 Day 60 visit. Prior to unblinding each participant's treatment assignment, the participant's available safety data will be reviewed and locked.

The Clinical Biostatistics department will generate the randomized allocation schedule(s) for study treatment assignment. Randomization will be implemented using IRT.

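### Because allocation is opened at the Day 60 visit before any procedure, SAEs and respiratory episodes first disclosed at that visit are assessed with the arm known

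*Combined protocol and SAP*

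**What the plan says.** - Section 4.1 fixes the order at the Day 60 visit: the participant's "treatment assignment will be unblinded at the Day 60 visit before any visit procedures".
- Section 6.3.3 sets the boundary between the two parts. "In Part 1 of this study (up to the Day 60 visit), a double-blinding technique will be used". Then: "Part 2 of this study (time of unblinding through duration of participation in the study) is conducted as open-label".
- The schedules follow that boundary. The Part 1 table is headed "Schedule of Activities RSV Season 1 Day 1 Up to Day 60 Visit" and leaves its Day 60 column empty apart from a cross-reference. The Day 60 procedures, including AE/SAE review, brief examination, vital signs and respiratory assessment if indicated, stand in the two open-label tables headed "Schedule of Activities RSV Season 1 Day 60 Visit Through End of RSV Season 1" (SoA 1.3.1.2 and 1.3.1.3).
- Section 3 defines the 42-day safety period as "safety data collected from Day 1 post Dose 1 through 14 days post Dose 2". Section 4.2.3 explains that the placebo second dose keeps the blind through that period.
- Section 9.2 says that, before each participant is unblinded, the participant's "available safety data will be reviewed and locked".

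**The concern.** The order in Section 4.1 separates when an event happens from when it is first assessed. An event can begin while everyone is blinded and still be first described to the site, graded, attributed and examined just after the parent and investigator have learned the arm.

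Three outcomes are open to this:

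- **SAEs.** They are a primary endpoint through RSV Season 1 (Sections 3 and 9.4.2).
- **Drug-relatedness.** Drug-related AEs and serious drug-related AEs are Tier 2 categories with between-group confidence intervals (Section 9.6.2, Table 7). Causality is the investigator's judgement (Section 10.3.5).
- **MALRI.** Signs seen at a study visit count if the investigator observes or confirms them (Table 1). The NP sample is taken only when signs are observed or confirmed (Section 8.2.2.2), so judgement comes before the objective PCR.

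Section 8.1.10 already accepts the principle. In an emergency, the investigator should try to record severity and relation to study intervention before the code is opened. The planned unblinding, which applies to every continuing participant, has no such step, and no reason is given for opening the allocation ahead of the procedures that do not depend on arm.

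**Working it through.** **Reproducing the plan's figure.** Dose 2 is nominally on Day 28, and the safety period runs 14 days beyond it: 28 + 14 = 42, the stated 42 days.

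**Inputs** (SoA 1.3.1.1 to 1.3.1.3), using simple differences of study-day numbers:

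- Dose 2 on day *d*, with *d* from 28 to 32.
- Day 42 call: Days 42 to 46, and at least 14 days after Dose 2, so from *d* + 14 to 46.
- Day 60 visit: *d* + 28 to *d* + 32.

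**Interval between the call and the visit**

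- Shortest: (*d* + 28) − 46 = *d* − 18.
- Longest: (*d* + 32) − (*d* + 14) = 18.

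| Dose 2 | Call | Day 60 visit | Interval |
|---|---|---|---|
| Day 28 | Days 42–46 | Days 56–60 | 56 − 46 = 10 to 60 − 42 = 18 days |
| Day 32 | Day 46 | Days 60–64 | 60 − 46 = 14 to 64 − 46 = 18 days |

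The permitted range is 10 to 18 days. Unblinding comes 14 to 18 days after the 42-day safety period ends (*d* + 28 − (*d* + 14) = 14; *d* + 32 − (*d* + 14) = 18). No part of that period overlaps with known allocation.

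**What is still collected in the interval**

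| Outcome | Status between the call and the Day 60 visit |
|---|---|
| Nonserious AEs, AESI | Collection closed 14 days after Dose 2 (Sections 8.4.1, 8.4.8) |
| SAEs | Still reportable; next dated review is at the Day 60 visit, after unblinding |
| Respiratory episodes | Weekly contacts and unscheduled visits continue blinded; assessment due within 3 days of onset or worsening, at latest 12, and may take place at a scheduled visit (Section 8.2.2.1) |

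An episode that began up to 12 days before the Day 60 visit can therefore be first examined there and still meet the sampling window for the main analysis (Section 9.5.1).

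**Rough size for MALRI.** The documents give no incidence by interval. Assume even risk over 150 days and the lowest and highest incidences in Table 8, with 500 per arm. Cases with onset in the last 12 days before the visit are then 500 × 0.045 × 12/150 = 1.8 to 500 × 0.0825 × 12/150 = 3.3 per arm. If risk in that stretch were twice the average, the figures would be 3.6 to 6.6. These are ceilings, because cases examined earlier under the blind must be taken out.

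**SAEs.** The documents give no expected SAE rate for this interval, so the number cannot be estimated.

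**The case against.** The case on the other side is substantial.

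- A reader might infer that the last weeks of the double-blind part are assessed unblinded. The documents do not support that. Part 2 begins at unblinding, the Day 60 procedures belong to Part 2, and surveillance up to that visit is blinded.
- A reader might also infer that Section 4.1 contradicts Section 9.2. It does not: Section 9.2 promises to lock only the data then available, not what is disclosed later.
- The period that the placebo dose is there to protect is protected. Solicited events, AESI and nonserious AEs after the first two doses close under the blind.
- Blinded capture in the interval is real. Parents are told to call about symptoms or any medical visit. AE/SAE review is also marked in the Part 1 weekly-contact column, headed Day 14, which may be meant to apply every week. SAEs go to the sponsor within 24 hours of the site learning of them, with causality assessed before the first transmission.
- Most later efficacy follow-up is open-label by design: Days 60 to 150 are 91 of 150 days (61%; 87/150 = 58% to 95/150 = 63% over the visit windows). The main analysis requires a central-laboratory PCR result, and no hypothesis is tested.

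All of this stands as a limit on size. It does not reach the remaining case: an SAE or episode not yet reported or assessed when the family arrives on Day 60. Nor is the accepted open-label follow-up a reason to give up blinded assessment of events that arose before it.

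**Conclusion.** The point holds in a narrow form. Events from the 10 to 18 days before the Day 60 visit that had not already reached the site are first elicited, graded, attributed or examined with the arm known. The interval measures opportunity, not bias. Dividing it by the 60 days of Part 1 would not give a share of blinded data lost, because most events in it should surface through blinded channels.

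Few events should be affected: a handful of MALRI cases per arm at most under the assumptions shown, and an unknown but probably small number of SAEs.

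Two assumptions matter:

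- SAEs in the interval count in the primary safety comparison. Section 9.6.2 places that comparison after the first two doses but gives no closing day for SAEs. They count in the primary SAE endpoint in any case.
- If AE/SAE review is done at every weekly contact, the interval since the last blinded review is shorter than 10 to 18 days.

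This is a worthwhile, inexpensive improvement, not a threat to the study's main conclusions.

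**What to change.** Change Section 4.1 and the Day 60 columns of SoA 1.3.1.2 and 1.3.1.3 so that the visit runs in this order:

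1. While still blinded, complete and time-stamp the AE/SAE review for the period since the last contact, with grade and causality.
2. In the same blinded step, complete the respiratory symptom review, with examination and NP sample if indicated.
3. Open the allocation.
4. Carry out the arm-specific procedures.

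Add a sentence to Section 9.2 that the entries from steps 1 and 2 are part of the data fixed before that participant is unblinded. A signed, time-stamped entry is enough; a full database lock during the visit is not needed.

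The cost is a small documentation step within one visit. No procedure is added. The boundary in Section 6.3.3 can stay, since Part 2 would still begin at the moment of unblinding.

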Visit Number/Title													See Section 8.13 for descriptions of study visits. Post-surgery follow-up visit for participants who undergo 1) ECMO or 2) surgical intervention and require cardiopulmonary bypass during the procedure for CHD during the RSV season and are recommended during Sponsor consultation to receive additional study intervention (Section 8.1.8.1). UNSCH for respiratory infection and AESI assessment and early withdrawal, if indicated.
RSV Season 1 Palivizumab Group Part 2 Scheduled Day and Window (Days):	60 ^a	74 ^a	90 ^{a,b}	104 ^{a,b}	120 ^{a,b}	134 ^{a,b}	150 (±5)	180 (±2 ^c)	240 (±5)	365 (+14) ^d	If indicated	If indicated	See SoA in Section 1.3.1.1 for activities before the Day 60 visit. Participant's treatment assignment will be unblinded at the Day 60 visit (28-32 days after Dose 2). ^a Doses 3-5 must be administered between 28-32 days after the previous dose. Safety follow-up TCs must be conducted 14 days (±2 days) after each dose. ^b For those who do not require a dose at the Day 90 or 120 visits, the respective visit(s) and the associated 14-day safety follow-up TC will not be conducted. ^c Continue weekly contact, each with a ±2-day window. ^d Participants continuing into RSV Season 2 will begin RSV Season 2 up to 4 weeks before the start of their second RSV season (246 to 393 days after RSV Season 1 Dose 1) (Section 4.2.1.1.1). See SoA in Section 1.3.2 for RSV Season 2. Participants not eligible for RSV Season 2 will be followed through the RSV Season 1 Day 365 TC.
Pharmacokinetics/Immunogenicity/Pharmacodynamics													
Venous Blood for MK-1654 PK									X ⁱ				ⁱ Participants continuing in RSV Season 2 will have blood sample collection for PK, ADA, and SNA at the Day 240 visit.
Venous Blood for ADA									X ⁱ				
Venous Blood for RSV SNA									X ⁱ				

ADA=antidrug antibodies; AE=adverse event; AESI=adverse event of special interest; CHD=congenital heart disease; ECMO=extracorporeal membrane oxygenation; eDiary=electronic diary; LAR=legally acceptable representative; NP=nasopharyngeal; PK=pharmacokinetics; RSV=respiratory syncytial virus; RT-PCR=reverse transcriptase-polymerase chain reaction; SAE=serious adverse event; SNA=serum neutralizing antibodies against RSV; SoA=Schedule of Assessments; TC=telephone call; UNSCH=unscheduled visit.

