4.2.1.5 Pharmacodynamic Endpoints

4.2.1.5.1 Serum Neutralizing Activity Against RSV

This study will also evaluate the effect of a single dose of MK-1654 on RSV serum neutralizing activity to model the relationship between SNA and efficacy. In this assay, serial dilutions of the participant's serum will be used to inhibit the entry of RSV into target cells in vitro. Total RSV serum neutralizing activity may be influenced by environmental exposure to RSV in addition to the presence of MK-1654. Moreover, the activity of MK-1654 may be inhibited by the presence of ADA. Therefore, unexpected changes in RSV serum neutralizing activity will be examined for associations with respiratory infection and ADA titer.

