5.1 Inclusion Criteria

A participant will be eligible for inclusion in the study if the participant:

Type of Participant and Disease Characteristics

1. Recommended to receive palivizumab in accordance with national or local (eg, state or provincial) guidelines or professional society recommendations, **and** meets 1 or more of the following criteria:

- a) Early or Moderate Pre-term Group (excluding participants with CLD or hemodynamically significant CHD): ≤ 35 weeks, 0 days gestational age*.

Note: Participants in the Early or Moderate Pre-term Group who meet the additional inclusion criteria for RSV Season 2, as described in Section 5.1.1, will be consented for participation in 2 RSV seasons.

- b) CLD/CHD Group:

- CLD Participants: have CLD of prematurity (also known as bronchopulmonary dysplasia), as defined by:
 - American Academy of Pediatrics [American Academy of Pediatrics Committee on Infectious Diseases 2014]: ≤ 32 weeks, 0 days gestational age* and require medical intervention/management (ie, supplemental oxygen, bronchodilators, or chronic systemic corticosteroids) for at least 28 days after birth, or
 - Other national or local guidelines or professional society recommendations
- CHD Participants: have hemodynamically significant CHD, as defined by:
 - American Academy of Pediatrics [American Academy of Pediatrics Committee on Infectious Diseases 2014]: Uncorrected or palliated cyanotic or

acyanotic disease associated with documented pulmonary hypertension (eg, systolic pulmonary arterial pressure ≥ 40 mmHg or $\geq 1/2$ systolic blood pressure) or a requirement for daily medication to manage congestive heart failure, or as diagnosed by a pediatric cardiologist

- Other national or local guidelines or professional society recommendations

Note: CLD and CHD participants will be consented for inclusion in 2 RSV seasons, as described in Section 5.1.1.

*Gestational age at birth as calculated by the treating physician or qualified healthcare provider at the time of delivery or as documented in the medical record at the time of birth (eg, acceptable methods include assessment using prenatal [obstetric and/or sonographic evaluation using biometric markers] or postnatal [Ballard or New Ballard] methods).

2. Is available to complete the follow-up period:

- Up to 575 days (180 days after RSV Season 2 dose) for participants eligible for RSV Season 2 dose of MK-1654, or

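### The palivizumab group's Season 2 baseline is drawn at Season 1 Day 240, up to about 5 months before the first MK-1654 dose, which weakens it as a predose reference for SNA

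*Combined protocol and SAP*

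**What the plan says.** Section 4.1 gives the palivizumab group's Day 240 draw a single purpose: continuing infants "will have blood sample collection at the Day 240 visit to serve as the baseline for RSV Season 2". The footnote to the schedule in Section 1.3.1.3 names the assays: "Participants continuing in RSV Season 2 will have blood sample collection for PK, ADA, and SNA at the Day 240 visit". The visit window is ±5 days.

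The Season 2 dose is timed at "246 to 393 days after Dose 1 in RSV Season 1 during a routine RSV season". For infants randomized to palivizumab, Section 4.1 notes that this is their first MK-1654.

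The Season 2 schedule (Section 1.3.2.1) and Table 10 plan blood only at Season 2 Days 7 and 150, and Section 8 counts two planned Season 2 draws. In Season 1, by contrast, PK, ADA and SNA are sampled predose at the dosing visit itself (Sections 1.3.1.1 and 8.13.2).

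On SNA, Section 4.2.1.5.1 says: "Total RSV serum neutralizing activity may be influenced by environmental exposure to RSV in addition to the presence of MK-1654". It plans to examine unexpected SNA changes for association with respiratory infection and ADA titer. Weekly contact ends at Day 180 and resumes only after the Season 2 dose.

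**The concern.** A baseline should describe the infant at the time of dosing. Here it describes the infant at a fixed Season 1 visit, while the dose follows at a time set by the calendar of the next RSV season. The interval therefore depends on enrollment date and differs systematically between early and late enrollees.

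If neutralizing activity changes between Day 240 and the dose, a Season 2 Day 7 or Day 150 SNA titer compared with that baseline mixes the MK-1654 effect with the earlier change. Waning before the dose would make the rise look too small; an infection before the dose would make it look too large. Among Season 2 infants only the palivizumab group has had no earlier MK-1654, so it is the group in which a clean before-and-after SNA comparison would be most informative. Section 2.3 expects about 300 infants in Season 2. If continuation is equal by arm (an assumption), about 150 come from this group.

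**Working it through.** **Reproducing the dosing window.** Section 4.1 starts enrollment 4 weeks (28 days) before onset and gives it "approximately a 17-week duration during a routine RSV season", which is 17 × 7 = 119 days. Enrollment thus runs from day −28 to day +91 relative to onset. The Season 2 dose is given "up to 4 weeks before the beginning of the" second season. Taking onsets 365 days apart, that is day 337 to 365 after the first onset.

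- Shortest interval: 337 − 91 = 246 days.
- Longest interval: 365 + 28 = 393 days.

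Both match the plan. As a cross-check, 393 + 180 + the 2-day contact window = 575 days, the stated maximum participation.

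**Gap from baseline to dose** (dose day minus Day 240 visit day).

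- Nominal: 246 − 240 = 6 to 393 − 240 = 153 days.
- With the ±5-day window: 246 − 245 = 1 to 393 − 235 = 158 days.

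**Gap by enrollment date (nominal).**

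| Enrolled relative to onset | Season 2 dose day | Gap (days) |
|---|---|---|
| −28 days | 365 to 393 | 125 to 153 |
| 0 | 337 to 365 | 97 to 125 |
| +91 days | 246 to 274 | 6 to 34 |

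**Typical gap.** The documents give no enrollment distribution. Assume enrollment E is uniform on −28 to 91 and dosing S is uniform on 337 to 365, so the means are 31.5 and 351.

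- Mean gap: 351 − 31.5 − 240 = 79.5 days.
- Gap over 90 days requires E < S − 330. The average probability is (351 − 330 + 28)/119 = 49/119 = 41%.
- Gap over 120 days requires E < S − 360. The average probability is (351 − 360 + 28)/119 = 19/119 = 16%.

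**Time without weekly surveillance.** From Day 180 to the dose: 246 − 180 = 66 to 393 − 180 = 213 days.

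**Which assays depend on the gap.**

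- PK: no MK-1654 has been given, so the true predose concentration is zero whenever the sample is drawn.
- ADA to MK-1654: no MK-1654 exposure occurs in the gap, and the documents link environmental RSV exposure only to SNA.
- SNA: the true titer can change in the gap.

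**Is the gap in season?** Section 4.2.1.1 treats 150 days as a typical temperate season. For enrollment at −28, 0 and +91 days, Day 240 falls 212, 240 and 331 days after onset. That is 62, 90 and 181 days after such a season ends, and the dose comes no later than the next onset. In a routine temperate season the whole gap is off-season. This limits new infection but not waning.

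**The case against.** The strongest reply is that no stated analysis is damaged. The Season 2 SNA and ADA endpoints are levels at Days 7 and 150, Season 2 PK is summarized descriptively by time point, and no change from baseline is specified. SNA is tertiary. This stands and limits the weight of the point. It does not explain why a sample whose only stated role is to be a baseline is not taken at the dosing visit.

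Intervening illness is also not wholly unobserved. Changes in medical history, which covers prior RSV infections, are recorded at Season 2 Day 1. SAEs are reported through study completion. The note in Section 5.2.1 allows dosing to be rescheduled if lower respiratory symptoms occurred in the preceding 7 days. These catch serious or remembered illness; they do not replace weekly contact, and they say nothing about waning.

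A reader might infer that blood is drawn needlessly from infants who turn out to be ineligible. The documents do not support that as a general complaint: Section 1.3.1.3 requires the Season 2 eligibility review before the Day 240 draw. Only infants who pass then and fail at Season 2 Day 1 are affected, and their number is not given.

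Against moving the draw, Sections 3 and 9.4.3 list Day 240 for ADA and SNA without naming an arm, so a listed time point might seem to be lost. That is weak: Day 150 is listed in the same way but is not drawn in this arm.

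**Conclusion.** The point holds as a modest design improvement confined to SNA. The designated baseline precedes the first MK-1654 dose by 6 to 153 days (1 to 158 with the window). The mean is about 80 days if enrollment and dosing are uniform over their windows. The range assumes a routine season and onsets 365 days apart.

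The size of any SNA error cannot be stated, because the documents give neither SNA titers nor a palivizumab half-life. Waning can matter anywhere. New infection matters mainly at tropical or subtropical sites, or where seasonality is disrupted, both of which Section 4.1 anticipates.

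A reader might infer that the Season 2 effect of MK-1654 cannot be separated from other change on any assay. The documents do not support that: PK, the only secondary endpoint of the three, is unaffected, and ADA to MK-1654 is hardly affected. Nor is a 5-month gap the rule. It needs enrollment 4 weeks before onset together with dosing at the next onset, and every Day 240 sample still precedes the dose.

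**What to change.** For palivizumab-group infants continuing to Season 2, move the 2.4 mL PK/ADA/SNA draw from Season 1 Day 240 to Season 2 Day 1, predose, after the eligibility recheck. The existing Section 8.13.2 provision for a failed predose draw can be reused. Leave the MK-1654 group's Day 240 draw in place, since it serves a stated PK endpoint.

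Amend Sections 4.1 and 4.2, the schedules in 1.3.1.3 and 1.3.2.1, Table 10, and the count of planned draws per season in Section 8. If the new time point is to be reported, add it to the Season 2 lists in Sections 3 and 9.4.3.

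The number of draws and the total volume do not change: 2.4 + 1.0 in Season 1 plus 3 × 2.4 in Season 2 = 10.6 mL, as now. Season 2 Days 1 and 7 together take 4.8 mL, below the 4-week limit of 2.4 mL/kg × 3 kg = 7.2 mL for a 3 kg infant.

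The costs are a venepuncture at the dosing visit, no baseline at all if that draw fails, and pre-Season 2 sampling times that differ between the arms.

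If the draw is not moved, state that pre-to-post Season 2 SNA change in this group will not be attributed to MK-1654 alone.
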